Appendix H GUIDANCE REGARDING POTENTIAL INTERACTIONS WITH CONCOMITANT MEDICATIONS

The use of any natural/herbal products or other "folk remedies" should be discouraged but use of these products (e.g., herbal supplement), as well as use of all vitamins, nutritional supplements, and all other concomitant medications must be recorded in the eCRF.

DZD9008 is an investigational drug for which no data on *in vivo* drug-drug interactions (DDI) are currently available. *In vitro* data have shown that the principal CYP enzymes responsible for the Phase I metabolism of DZD9008 are CYP 3A4/5, and glutathione conjugation may be alternative pathway for DZD9008 metabolism.

In vitro DZD9008 showed either no inhibition or a low level reversible inhibition of CYPs 1A2, 2A6, 2B6, 2C8, 2C9, 2C19, 2D6, 2E1, 3A4/5 activity. DDI risk is considered low with these CYP enzymes, although the risk of a clinical interaction via inhibition CYP2D6 and intestinal CYP3A4 cannot be excluded at clinically relevant exposure.

There was not time dependent inhibition observed for DZD9008 *in vitro* with CYPs 1A2, 2C9 and 2C19. Time dependent inhibition was observed for CYP2D6 only at 50 μ M and CYP3A4/5 at both 10 and 50 μ M, however at clinically relevant exposure of DZD9008 the risk of a clinically meaningful drug interaction arising from CYP3A4/5 inhibition is minimal.

DZD9008 was shown to be an inhibitor of the active efflux transport protein P-gp and BCRP. It has also been determined to be an inhibitor of the active uptake transport mediated by OATP1B1. A clinical meaningful interaction with both intestinal P-gp, BCRP and OATP1B1 transporter cannot be excluded.

Restrictions regarding drug affecting CYP3A4 metabolism

CYP3A4/5 is considered to be the predominant metabolic pathway, thus modulation of CYP3A4/5 activity may increase or decrease exposure to DZD9008, respectively. In clinical DDI study, when co-administered with multiple doses of strong CYP3A4 inhibitor itraconazole, DZD9008 C_{max} and AUC increase by 32% and 51%, respectively. DZD9008 C_{max} and AUC decrease by 38% and 48%, respectively, when co-administered with multiple doses of strong CYP3A4 inducer carbamazepine.

Strong inhibitors and strong inducers of CYP3A4/5 should not be combined with DZD9008. Moderate inhibitors and inducers of CYP3A4/5 are permitted but caution should be exercised, and patients monitored closely for possibly drug interactions. Strong inhibitors or inducers of CYP3A4 should be stopped at least 1 week for inhibitors or 2 weeks for inducers before the first dose of DZD9008 (Table 23 & Table 24).

These lists are not intended to be exhaustive, and a similar restriction will apply to other agents that are known to strongly modulate CYP3A4 activity. Appropriate medical judgment is required. Please contact Dizal with any queries you have on this issue.

If the investigator feels that concomitant administration of medications or herbal supplements that strongly modulate CYP3A4/5 is essential during the trial, DZD9008 treatment should be discontinued.

Table 23 Drugs that are strong inhibitors of CYP3A4

Contraindicated drugs	Withdrawal period prior to DZD9008 start
Boceprevir, clarithromycin, conivaptan,	1 week
grapefruit juice*, indinavir, itraconazole,	
ketoconazole, lopinavir/RIT, mibefradil,	
nefazodone, nelfinavir, posaconazole, ritonavir,	
saquinavir, telaprevir, telithromycin,	
Voriconazole, elvitegravir/RIT, fluconazole	

^{*} Double-strength grapefruit juice

Table 24 Drugs that are strong inducers of CYP3A4

Contraindicated drugs	Withdrawal period prior to DZD9008 start
Avasimibe, Carbamazepine, phenobarbital, phenytoin, Rifampicin, rifabutin, rifapentin St John's Wort, Phenobarbitone	2 weeks

Drugs whose exposure may be affected by DZD9008 that Dizal considers may be allowed with caution, see Table 25.

In vitro data shows that DZD9008 is a weak inhibitor of CYP3A4/5, DZD9008 has the potential to increase the exposure of CYP3A4/5 substrate whose absorptive process is restricted by CYP3A4/5 metabolism in the intestine which includes some of the statins.

DZD9008 induces CYP3A4 and 2C8 but not CYP1A2, 2B6, 2C9 and 2C19 isoforms *in vitro* in human primary hepatocytes. The exposure of co-medications where disposition is dependent on CYP3A4, or CYP2C8 isoforms and P-gp which may also be induced, may be reduced when co-administrated with DZD9008.

CYP2C8 and P-gp substrate

Sensitive CYP2C8 and P-gp substrate with narrow therapeutic range are permitted but caution should be exercised, and patients monitored closely for possible drug interactions.

CYP3A4 substrate and P-gp and/or BCRP substrates

In vitro data suggests DZD9008 has the potential to cause drug interactions at the intestinal level through CYP3A4. It has also been shown that there is a potential for a DDI when dosed with sensitive substrates of P-gp, BCRP or OATP1B1. DDI was predicted following more conservative approaches recommended by EMA and PMDA. Although a potential interaction with DZD9008 and OATP1B3, MATE1 and MATE2 K substrates cannot be ruled out, the

^{*} Patients should abstain from eating large amounts of grapefruit and Seville oranges (and other products containing these fruits e.g., grapefruit juices or marmalade) during the study

Date: July 24,2023

predicted values are close to cut-off and therefore DDI risks with these transporter substrates are considered to be low. Table 25 outlines some of the drugs that are sensitive substrates of CYP3A4, CYP2C8, P-gp, BCRP, OATP1B1/3, MATE1 and MATE2 K. This list is not intended to be exhaustive, and a similar restriction will apply to other agents that are known to depend on CYP3A4 and/or transporter proteins for disposition and/or metabolism. Appropriate medical judgement is required. Please contact Dizal with any queries you have on this issue.

Patients taking concomitant medications such as statins whose disposition is dependent upon Breast Cancer Resistance Protein (BCRP) and which have a narrow therapeutic index should be closely monitored for signs of changed tolerability as a result of increased exposure of the concomitant medication whilst receiving DZD9008. If the patient experiences any potentially relevant AEs suggestive of muscle toxicity including unexplained muscle pain, tenderness or weakness, particularly if accompanied by malaise or fever, statins must be stopped, and any appropriate further management should be taken.

Exposure, pharmacological action and toxicity may be increased or Table 25 decreased by DZD9008

Warning of possible interaction	Advice				
CYP3A4 substrate: alfentanil, cyclosporine, dihydroergotamine, ergotamine, everolimus, fentanyl, pimozide, quinidine, sirolimus and tacrolimus	Drugs are permitted but caution should be exercised, and patients monitored closely for possible drug interactions. Please refer to full prescribing information for all drugs prio to co-administration with DZD9008.				
CYP2D6 substrate : Pimozide, thioridazine					
CYP2C8 substrate: Repaglinide					
P-gp substrate: Digoxin	Monitor for increased digoxin concentrations if increase in intolerability is observed due to increased systemic exposure. Monitor for adverse reactions if concomitant use of DZD9008 with other P-gp substrates with a narrow therapeutic index cannot be avoided				
BCRP substrate : Methotrexate, topotecan, or irinotecan, rosuvastatin, sulfasalazine	Drugs are permitted but caution should be exercised, and patients monitored closely for possible drug interactions. Please refer to full prescribing information for all drugs prior				
MATE1 and MATE2-K substrate: metformin	to co-administration with DZD9008.				
OATP1B1/3: atorvastatin, pitavastatin, pravastatin, simvastatin acid					

Drugs that may prolong QT interval

The drugs listed in this section are taken from information provided by The Arizona Center for Education and Research on Therapeutics and The Critical Path Institute, Tucson, Arizona and Rockville, Maryland. Ref: https://crediblemeds.org/.

Drugs known to prolong QT interval

The following drugs are known to prolong QT interval or induce Torsades de Pointes and should not be combined with DZD9008. Recommended withdrawal periods following cessation of treatment with these agents are provided in Table 26 & Table 27.

Table 26 Drugs prolonging QT interval

Contraindicated drug	Withdrawal period prior to DZD9008 start
Clarithromycin, droperidol, erythromycin, procainamide	2 days
Cisapride, disopyramide, dofetilide, domperidone, ibutilide, quinidine, sotalol, sparfloxacin, thioridazine	7 days
Bepridil, chlorpromazine, halofantrine, haloperidol, mesoridazine	14 days
Levomethadyl, methadone, pimozide	4 weeks
Arsenic trioxide	6 weeks*
Pentamidine	8 weeks
Amiodarone, chloroquine	1 year

^{*} Estimated value as pharmacokinetics of arsenic trioxide has not been studied

Drugs that may possibly prolong QT interval

The use of the following drugs is permitted (notwithstanding other exclusions and restrictions) provided the patient has been stable on therapy for the periods indicated.

Table 27 Drugs that may prolong QT interval

Drug	Minimum treatment period on medication prior to DZD9008 start
Alfuzosin, chloral hydrate, ciprofloxacin, dolasetron, foscarnet, galantamine, gemifloxacin, isridipine, ketoconazole, levofloxacin, mexiletine, nicardipine, octreotide, ofloxacin, ondansetron, quetiapine, ranolazine, telithromycin, tizanidine, vardenafil, venlafaxine, ziprasidone	2 days
Amantadine, amitriptyline, amoxapine, clozapine, doxepin, felbamate, flecainide, fluconazole, fosphenytoin, gatifloxacin, granisetron, imipramine, indapamide, lithium, moexipril/HCTZ, moxifloxacin, risperidone, roxithromycin, sertraline, trimethoprimsulfa, trimipramine, voriconazole	7 days
Azithromycin, citalopram, clomipramine, itraconazole, nortriptyline, paroxetine, solifenacin, tacrolimus	14 days
Fluoxetine	5 weeks
Protriptyline	6 weeks

	Drug	Minimum treatment period on medication prior to DZD9008 start
Tamoxifen		8 weeks

Restriction regarding drugs may affect DZD9008 absorption

DZD9008 exhibited pH-dependent solubility, thus the absorption may be affected by altered intragastric pH. When intragastric pH is elevated, DZD9008 GI solubility, bioavailability and eventually treatment efficacy may be influenced. To avoid reduced oral absorption of DZD9008 and safeguard optimal DZD9008 therapy, intake of gastric acid suppressive agents relative to DZD9008 treatment is suggested to be managed (Table 28).

Table 28 Gastric acid suppressive agents that may affect DZD9008 exposure

Type of gastric acid suppressive agents	Dosage management relative to DZD9008 administration				
Proton pump inhibitors	PPIs should be avoided.				
H2- antagonists	DZD9008 should be taken at least 2 h before or 10 h after the H2- antagonist intake.				
Antacids	DZD9008 should be administrated at least 2 h before or 2 h after antacid intake.				

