- 3. All patients must avoid concomitant use of medications herbal supplements and/or ingestions of foods with known potent inducer/inhibitory effects on CYP3A4 activity whenever feasible. Such drugs must have discontinued for a period of 1 week (CYP3A4 inhibitors) or 2 weeks (CYP3A4 inducers) prior to first administration of DZD9008. Guidance on medications to avoid, medications that require close monitoring and on washout periods is given in Appendix H. Patients may receive any medication that is clinically indicated for treatment of adverse events. All concomitant medications should be captured on the eCRF.
- 4. Patients should abstain from eating large amounts of grapefruit and Seville oranges (and other products containing these fruits, e.g., grapefruit juice or marmalade) during the study, e.g., no more than a small glass of grapefruit juice (120 mL) or half a grapefruit or 1 to 2 teaspoons (15 g) of Seville orange marmalade daily.

Date: July 24,2023

- 5. Patients should avoid donating blood whilst participating in studies of DZD9008 and for at least 12 weeks after receiving the last dose of the study treatment.
- 6. Patients who wear contact lens must discontinue wearing their lenses if they have any mild to moderate eye symptoms (CTCAE grade ≤ 2) while receiving treatment with DZD9008 until at least one week after symptoms have resolved. If a patient has a recurrence of eye symptoms or experiences any severe (CTCAE grade ≥ 3) ocular events, they must discontinue wearing their contact lenses until at least one week after treatment with DZD9008 is permanently discontinued. Patients must not use any eye drops or ointment for treatment of eye symptoms, unless agreed by a study doctor, at any time during the study until 1 week after DZD9008 has been permanently discontinued, Patient should consult the clinic promptly if they have any concerns.
- 7. Patients require anticoagulation and anti-platelet therapy, i.e., with Warfarin, heparin etc. while receiving DZD9008 may be at increased risk of hemorrhage. They should be monitored for any signs of bleeding.

For restrictions relating to concomitant medications, see next Section 4.3.1.

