5.2.2.9 CYP450 induction/inhibition

All patients must try to avoid concomitant use of medications, herbal supplements and/or ingestions of foods with known potent inducer or inhibitors on CYP3A4 activity whenever feasible. Such drugs must have been discontinued for a period of 1 week (CYP3A3 inhibitors) or 2 weeks (CYP3A4 inducers) prior to first administration of DZD9008. Patients taking concomitant medications whose disposition is dependent upon intestinal CYP3A4 and/as or transporter proteins and which have a narrow therapeutic index should be closely monitored for signs of changed tolerability as a result increased exposure of the concomitant medication whilst receiving DZD9008. Guidance on medications to avoid, medications that require close monitoring and on washout periods is given in Appendix H. If medically feasible, patients taking regular medication, with the exception of potent inhibitors or inducers of CYP3A4, should be maintained on them throughout the study period. Patients may receive any medication that is clinically indicated for treatment of adverse events.

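### The body of the protocol lets a site treat an adverse event with a strong CYP3A4 modulator without saying that DZD9008 stops; Appendix H says it should

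*Protocol*

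**What the plan says.** **Body text.** Section 4.3 item 3, Section 4.3.1 and Section 5.2.2.9 share the same structure. Each asks patients to avoid potent CYP3A4 modulators, but with a qualifier; in Section 5.2.2.9 the object is "known potent inducer or inhibitors on CYP3A4 activity whenever feasible". Each refers to Appendix H for guidance on drugs to avoid. Each also contains the sentence "Patients may receive any medication that is clinically indicated for treatment of adverse events", with no exception attached. Sections 4.3.1 and 5.2.2.9 do except potent CYP3A4 inhibitors and inducers, but only from the advice to keep patients on their regular medication.

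**Appendix H.** The rule here is not qualified by feasibility: "Strong inhibitors and strong inducers of CYP3A4/5 should not be combined with DZD9008". If the investigator considers that a strong modulator "is essential during the trial, DZD9008 treatment should be discontinued". There is no separate rule for adverse event treatment. For doubts about the drug lists it adds "Please contact Dizal with any queries you have on this issue".

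**Appendix H, two drug lists.** Table 23 contraindicates strong inhibitors and sets a one-week withdrawal before DZD9008 starts; its entries include "grapefruit juice*, indinavir, itraconazole". Table 27 lists drugs that may prolong QT under a different rule: "The use of the following drugs is permitted (notwithstanding other exclusions and restrictions) provided the patient has been stable on therapy" for a stated minimum period before DZD9008 starts. Its two-day row includes "isridipine, ketoconazole, levofloxacin".

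**The concern.** A patient on DZD9008 develops an adverse event for which the investigator wants a strong CYP3A4 inhibitor, such as an azole antifungal or clarithromycin. The body text says the drug may be given and that avoidance applies where feasible. Appendix H says DZD9008 should stop. Two sites could manage the same patient differently and each point to the protocol.

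At stake are patient management and exposure. The situation is foreseeable: Appendix I advises oral antibiotics for six weeks for grade 3 rash, and considering prophylactic antibiotics for complicated diarrhea, without naming agents or adding a CYP3A4 caution. Table 23 includes clarithromycin and telithromycin. The documents do not show how often a strong modulator would be chosen.

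**Working it through.** **1. The texts side by side.**

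| Question | Sections 4.3 item 3, 4.3.1, 5.2.2.9 | Appendix H |
|---|---|---|
| Strength of the restriction | Avoid where feasible | Do not combine |
| Drug needed for an adverse event | Any indicated drug allowed, no exception | No separate rule |
| DZD9008 if a strong modulator is essential | Not stated | Discontinue |
| Which text governs | Not stated; Appendix H is called guidance | Not stated |

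Section 5.2.2.4 shows how the adverse event sentence can be read. For QT-prolonging drugs it states the restriction, cites Appendix H, and introduces the same permission with *but*. There the permission works as an exception to the Appendix H restriction. A site could read it the same way for CYP3A4.

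**2. Size at steady state.** Inputs: itraconazole raises AUC by 51% and carbamazepine lowers it by 48% (Appendix H); exposure is roughly dose-proportional over 50–400 mg (Section 2.3.5); Part B starting doses are 200 and 300 mg. The equivalent dose is the dose times the AUC ratio.

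- 300 mg with inhibitor: 300 × 1.51 = 453 mg
- 200 mg with inhibitor: 200 × 1.51 = 302 mg
- 300 mg with inducer: 300 × (1 − 0.48) = 156 mg
- 200 mg with inducer: 200 × (1 − 0.48) = 104 mg

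Only the first lies outside the studied range, and 453 mg extrapolates proportionality above 400 mg.

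**3. Size over a short course.** A course of treatment for an adverse event may end before steady state. Assumptions: one compartment, half-life 50 h (Section 5.1.4), once-daily 300 mg from steady state, full 1.51-fold effect from the first day (an upper bound), and a course of 5–14 days. The documents give neither onset time nor course length. With k₀ = ln 2 / 50 per hour, the effect is placed either on clearance (k = k₀/1.51, half-life 75.5 h) or on bioavailability (F = 1.51, k = k₀). Daily AUC is expressed as a 300-mg-based equivalent dose.

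| Course | Average, clearance | Average, bioavailability | Last day, clearance | Last day, bioavailability |
|---|---|---|---|---|
| 5 days | 361 mg | 390 mg | 397 mg | 424 mg |
| 7 days | 376 mg | 403 mg | 417 mg | 438 mg |
| 14 days | 406 mg | 426 mg | 445 mg | 452 mg |

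Daily exposure first passes 400 mg-equivalent on day 6 (clearance) or day 4 (bioavailability).

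**4. Overlap of the two lists.** Table 23 has 19 entries and Table 27 has 55. Five drugs are in both: ketoconazole and telithromycin (2 days of stable use), fluconazole and voriconazole (7 days), and itraconazole (14 days). Taken literally, itraconazole cannot be both withdrawn for a week and taken for at least 14 days before DZD9008 starts.

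**The case against.** **The texts can be reconciled.** The permission covers which drug the patient may take; it does not say DZD9008 continues. Appendix H says what happens to DZD9008. A site can treat the event and stop DZD9008, satisfying both, and the referral to Appendix H stands close to the permission in all three sections. This is fair: the problem is an ambiguity, and a reader who infers that the texts cannot both be followed goes too far. But the body never states the reconciled reading, its feasibility qualifier implies that combined use is sometimes acceptable, and Section 5.2.2.4 uses the same sentence as an exception.

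**Table 27 is not a route to co-dosing.** A reader might infer that its bracketed override lets patients take five contraindicated inhibitors with DZD9008. The documents do not support that. Table 27 covers only drugs on which the patient was already stable before DZD9008 started. Exclusion criterion 1 in Section 4.2 bars potent CYP3A inhibitors within one week before the first dose, and Sections 4 and 5.3.1 allow no exceptions to eligibility. A patient already on the drug is ineligible, and one who starts it later cannot meet the condition. What remains is list clean-up.

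**The size is conditional.** The protocol gives no frequency, Section 5.1.4 describes 50–400 mg as well tolerated, and Section 5.1.5 has interruption and reduction rules. All of this stands and keeps the point small. Section 5.1.4 also reports more interruptions and reductions at 400 mg, so exceeding that exposure is not neutral.

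**Conclusion.** The inconsistency is real and minor. A site that follows the body text could continue DZD9008 alongside a strong CYP3A4 modulator where Appendix H says to stop. Only 300 mg with a strong inhibitor takes a starting dose beyond the studied exposure: at most about 453 mg-equivalent at steady state, and 361–426 mg on average over a 5–14 day course, under the assumptions above. The number affected is unknown and probably small, because users of potent modulators are excluded at entry.

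A reader might infer that the trial's results are threatened. The documents do not support this. Tumor assessments continue after discontinuation for reasons other than progression (Protocol Sections 5.3 and 6.3.6.2), and the primary estimand uses those data under a treatment policy strategy (SAP Section 2.1.1), so the effect on ORR is small. The PK set leaves out patients with deviations thought to affect the PK analysis (SAP Section 3.5), which limits the effect on PK summaries.

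**What to change.** 1. In Sections 4.3 item 3, 4.3.1 and 5.2.2.9, add after the adverse event sentence: *except strong CYP3A4 inhibitors or inducers, which should not be given together with DZD9008; if one is essential, DZD9008 is stopped per Appendix H.*
2. In Appendix H, the sponsor states whether that stop is an interruption or permanent. Section 5.3 bars restarting after permanent discontinuation, so without this a short course of an antifungal could end a responder's therapy by default. Any restart interval is the sponsor's clinical choice.
3. Clean-up: remove the five shared drugs from Table 27, or make its permission subject to the other restrictions. This changes no eligible patient's treatment.

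**Cost.** The edits are short and need no new data. They do need a protocol amendment, with ethics committee and, where applicable, regulatory approval before use (Appendix D), and a note to sites. A few patients will interrupt or stop DZD9008 who might otherwise have continued, which Appendix H already calls for.

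### Appendix H permits pimozide and quinidine (and apparently thioridazine) with caution in Table 25, contraindicates all three in Table 26, and never says which table governs on treatment

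*Protocol*

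**What the plan says.** All the conflicting text is in Protocol Appendix H.

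- **Lead-in to Table 25:** "Drugs whose exposure may be affected by DZD9008 that Dizal considers may be allowed with caution, see Table 25".
- **Table 25, CYP3A4 substrate row:** the list ends "fentanyl, pimozide, quinidine, sirolimus and tacrolimus". The advice is "Drugs are permitted but caution should be exercised, and patients monitored closely for possible drug interactions", followed by "Please refer to full prescribing information for all drugs".
- **Table 25, CYP2D6 substrate row:** "Pimozide, thioridazine". The advice cell is blank in the text available.
- **Scope of Table 25:** "Table 25 outlines some of the drugs that are sensitive substrates of CYP3A4, CYP2C8, P-gp, BCRP, OATP1B1/3, MATE1 and MATE2 K". CYP2D6 is not named there.
- **Lead-in to Table 26:** its drugs "are known to prolong QT interval or induce Torsades de Pointes and should not be combined with DZD9008". The drug column is headed as contraindicated.
- **Table 26, 7-day withdrawal row:** "Cisapride, disopyramide, dofetilide, domperidone, ibutilide, quinidine, sotalol, sparfloxacin, thioridazine". Pimozide is in the 4-week row.

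Elsewhere in the protocol, exclusion criterion 5 (Section 4.2) rules out patients taking medication known to prolong QT. Section 5.2.2.4 restricts such drugs during the study only as far as feasible, refers to Appendix H, and allows any medication clinically indicated to treat an adverse event.

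**The concern.** A site pharmacist or investigator who looks up pimozide or quinidine in Table 25 finds what reads as a complete answer: the drug may be given with caution. Nothing there points to the prohibition in Table 26. The two tables cannot both be followed, and the protocol does not rank them.

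What is at stake is mainly the drugs' own QT and Torsades risk. A rise in their exposure is secondary: Appendix H rates the CYP inhibition risk as low, calls the CYP3A4/5 inhibition risk minimal, and notes that CYP3A4 induction could lower the exposure of substrates. The cardiac background is not entirely clean. Section 2.3.2 reports that DZD9008 inhibits hERG and is active at three other cardiac ion channels, although single-dose telemetry in dogs showed no notable cardiovascular effect.

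**Working it through.** **1. Count the overlap.** Drug names were taken from the two tables and compared.

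- Table 25 entries by row: CYP3A4 10, CYP2D6 2, CYP2C8 1, P-gp 1, BCRP 5, MATE 1, OATP1B1/3 4. The sum is 10 + 2 + 1 + 1 + 5 + 1 + 4 = 24. Pimozide appears twice, so there are 24 − 1 = 23 distinct drugs.
- Table 26 entries by withdrawal period, from 2 days to 1 year: 4 + 9 + 5 + 3 + 1 + 1 + 2 = 25 distinct drugs.
- Drugs in both tables:

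| Drug | Row in Table 25 | Advice in Table 25 | Withdrawal in Table 26 |
|---|---|---|---|
| Pimozide | CYP3A4 and CYP2D6 | Permitted with caution (CYP3A4 row) | 4 weeks |
| Quinidine | CYP3A4 | Permitted with caution | 7 days |
| Thioridazine | CYP2D6 only | Blank; permitted by inference | 7 days |

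The overlap is 3 of 23. Counting only the CYP3A4 row, whose advice cell is filled, it is 2. The inference for thioridazine rests on the lead-in, which covers the whole of Table 25, and on what looks like a merged advice cell.

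**2. Look for text that ranks the tables.**

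- Exclusion criterion 5 settles entry. Section 4 applies the criteria at the time study treatment starts, so they do not govern a drug begun later.
- Section 5.2.2.4 leans towards restriction, but only as far as feasible, and it sends the reader back to Appendix H.
- Sections 4.3.1 and 5.2.2.9 deal with potent CYP3A4 inhibitors and inducers. Section 5.2.2.9 also asks for monitoring of narrow-index substrates. Neither addresses QT drugs.
- One clause in Appendix H does say how a permission relates to other restrictions, but it introduces Table 27. None of the three drugs is in Table 27.
- Section 5.3.1 asks the investigator to inform the Study Physician when a patient no longer meets study criteria. It does not rank the tables.

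No precedence rule was found.

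**3. Time to the next scheduled ECG (Part B).** Section 6.3.5.1 schedules ECGs on Cycle 1 Days 1, 8 and 15 and on Day 1 of each later cycle. Table 14 gives 21-day cycles. The study days are therefore 1, 8, 15, 22, 43, 64, 85 and so on, with gaps of 7, 7, 7, 21, 21, 21 days. Table 14 allows ±2 days per visit from Cycle 2 Day 1, so the longest gap is 21 + 2 + 2 = 25 days.

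**The case against.** The strongest reply is that the tables answer different questions. Table 25 concerns changes in exposure and Table 26 concerns QT risk. Safety restrictions are usually read together, so permission under one heading does not lift a prohibition under the other. The clause before Table 27 supports this: where Appendix H permits use despite other restrictions, it says so, and Table 25 has no such wording. A cautious investigator would probably follow Table 26. This is a plausible reading, but it is an inference. Table 25 permits the drugs outright and does not limit the permission to exposure.

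Safeguards also exist. Table 25 asks for close monitoring and use of the prescribing information. The surrounding text calls for medical judgement and offers contact with the sponsor. An ECG is required when a cardiac adverse event occurs, and Section 5.1.5 interrupts treatment for confirmed QTc above 500 msec or an increase above 60 msec. These points stand, and they are why the likely harm is small. The ECG and interruption rules, however, act after the combination has been given. The 21-day gap would apply to any newly started drug. It shows how long co-administration might go unchecked by a scheduled ECG; the table overlap does not cause it.

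The reservation about thioridazine also stands: the explicit conflict is two drugs.

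Finally, deleting names would remove a listed interaction warning if one of these drugs were used to treat an adverse event. Little is lost for pimozide and quinidine, because Appendix H says the list is not exhaustive and extends to other CYP3A4-dependent agents. That sentence does not cover CYP2D6, so thioridazine would lose its only entry.

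**Conclusion.** The contradiction is real. Two drugs are explicitly permitted in Table 25 and contraindicated in Table 26. A third, thioridazine, joins them if the blank advice cell is read with the lead-in or as merged with the row above. The gap concerns drugs started during treatment only, since entry is settled by exclusion criterion 5.

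The practical size is limited. The documents do not say how many patients might start one of these drugs, and the existing safeguards reduce the likely harm. Sample size, type I error and the efficacy analyses are untouched. The point still deserves correction, because the guidance concerns Torsades risk, is wrong as written in one of two places, and costs almost nothing to repair.

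**What to change.** Delete pimozide, quinidine and thioridazine from Table 25. Under that table, add a note that for any drug also appearing in Table 26 the Table 26 contraindication prevails. Send sites a short clarification. The note is still useful after the deletions, because Table 25 is open-ended and could be read to take in other Table 26 drugs. If the sponsor prefers to keep the named interaction warnings, the note alone would remove the contradiction.

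Do not resolve the overlap by taking the drugs out of Table 26, since that would clash with exclusion criterion 5. The allowance in Section 5.2.2.4 for medication needed to treat adverse events is a separate matter and is left unchanged.

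The cost is three names deleted, one sentence added and one message to sites. Data collection and analysis do not change.

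### Appendix H, Table 27 of the protocol permits five strong CYP3A4 inhibitors that Table 23 contraindicates and exclusion criterion 1 bars

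*Protocol*

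**What the plan says.** Appendix H of the protocol deals with strong CYP3A4 inhibitors first. Its text states "Strong inhibitors and strong inducers of CYP3A4/5 should not be combined with DZD9008". Table 23 then lists the contraindicated inhibitors, with a one-week withdrawal before the first dose. If a strong modulator becomes essential during the trial, the instruction is to discontinue DZD9008.

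The main text agrees. Section 4.2, criterion 1, excludes patients on potent CYP3A inhibitors within one week before the first dose, and Section 4 allows no exceptions to the eligibility criteria. Sections 4.3 (item 3), 4.3.1 and 5.2.2.9 repeat the one-week stop and refer sites to Appendix H for the drugs to avoid and their washouts.

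Later in the same appendix, Table 27 lists drugs that may prolong the QT interval. Its lead-in reads "The use of the following drugs is permitted (notwithstanding other exclusions and restrictions", provided the patient has been stable on therapy for the period shown. Its column heading is "Minimum treatment period on medication prior to DZD9008 start". The relevant entries are:

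- 2 days: "isridipine, ketoconazole, levofloxacin" and "ranolazine, telithromycin, tizanidine"
- 7 days: "flecainide, fluconazole, fosphenytoin" and "trimethoprimsulfa, trimipramine, voriconazole"
- 14 days: "Azithromycin, citalopram, clomipramine, itraconazole, nortriptyline, paroxetine, solifenacin, tacrolimus"

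**The concern.** *Notwithstanding* means *despite*. Read literally, Table 27 overrides the CYP3A4 rules for every drug it lists, including drugs that Table 23 forbids. The two tables also ask for opposite things: Table 23 wants the drug stopped for a week, and Table 27 wants it established and ongoing when DZD9008 starts.

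A site that looks up itraconazole in Table 27 could therefore start DZD9008 in a patient taking a strong CYP3A4 inhibitor. That patient would have raised DZD9008 exposure together with a drug the protocol itself lists as possibly QT-prolonging. Section 2.3.2 also reports that DZD9008 inhibits the hERG channel.

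This is a safety-wording error. It has no bearing on the ORR analysis, the error rate or the power, and no confounding between the dose arms is claimed.

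**Working it through.** **Overlap of the tables.** Table 23 has 19 entries and Table 27 has 55. Comparing them drug by drug gives exactly five in common:

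| Drug | Table 23 | Table 27 |
|---|---|---|
| Ketoconazole | contraindicated; off for 1 week | permitted; on for at least 2 days |
| Telithromycin | contraindicated; off for 1 week | permitted; on for at least 2 days |
| Fluconazole | contraindicated; off for 1 week | permitted; on for at least 7 days |
| Voriconazole | contraindicated; off for 1 week | permitted; on for at least 7 days |
| Itraconazole | contraindicated; off for 1 week | permitted; on for at least 14 days |

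Table 27 shares no drug with Table 24 (strong inducers) or Table 26 (drugs known to prolong QT).

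**Which side is wrong.** Criterion 1, the no-exceptions rule in Section 4, the one-week stop in Sections 4.3, 4.3.1 and 5.2.2.9, and the CYP3A4 text of Appendix H all agree with Table 23. Criterion 1 names a class rather than drugs; Table 23 is where the protocol places these five in that class. Only the Table 27 clause points the other way.

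**A related cross-reference.** The paragraph on drugs known to prolong QT says they must not be combined with DZD9008 and cites Tables 26 and 27 for their withdrawal periods. Table 27 holds no withdrawal periods. It gives minimum periods on treatment for permitted drugs.

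**Size of the exposure effect.** Inputs:

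- Itraconazole raises DZD9008 C_max by 32% and AUC by 51% (Appendix H).
- Multiple-dose exposure is approximately dose-proportional over 50 to 400 mg (Section 2.3.5).
- The Part B doses are 200 mg and 300 mg.

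The dose with equivalent exposure is the dose multiplied by (1 + rise):

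- AUC at 200 mg: 200 × 1.51 = 302 mg, inside the studied range.
- AUC at 300 mg: 300 × 1.51 = 453 mg, above the studied range and so an extrapolation.
- Rise that takes 300 mg to the 400 mg AUC: 400/300 − 1 = 33%, which is below 51%.
- Largest dose whose AUC stays at or below the 400 mg level: 400/1.51 = 265 mg.
- C_max at 200 mg: 200 × 1.32 = 264 mg.
- C_max at 300 mg: 300 × 1.32 = 396 mg, just under 400 mg.

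The safe reading at 300 mg is that AUC passes the 400 mg level; the figure of 453 mg should not be relied on. Section 5.1.4 reports more dose interruptions and reductions at 400 mg than at other doses, and a positive relation between exposure and gastrointestinal events. The same section also describes 50 to 400 mg as well tolerated.

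**The case against.** The strongest reply is that Section 4 controls eligibility. No patient may be treated while meeting an exclusion criterion, criterion 1 bars potent CYP3A inhibitors, and Appendix H is only guidance. The authors probably meant *subject to*, since Table 27 concerns QT alone, and that reading removes the conflict. Part B also has QT safeguards: a QTc entry limit, triplicate ECGs at repeated visits, and interruption for QTc above 500 msec or more than 60 msec above baseline. Deleting the five drugs as well as rewording would remove their only mention as possibly QT-prolonging.

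Much of this stands as a limit on the risk. A site that applies criterion 1 will not make the error. It is also fair that only the pre-dose stop is firm: on study, Sections 4.3, 4.3.1 and 5.2.2.9 ask for avoidance where feasible and allow any medication needed to treat an adverse event.

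It does not remove the error. The text says the opposite of *subject to*. On the kinder reading the five entries could never apply before the first dose, so they still do not belong in a list of permitted drugs. Sites are sent to Appendix H to find out which drugs to avoid, and there they find both answers. The QT safeguards do nothing about raised DZD9008 exposure. The point about losing the QT information is reasonable, and a footnote to Table 23 meets it.

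**Conclusion.** The concern holds, and it should be fixed. Five drugs are both contraindicated and permitted in one appendix, and the only precedence wording there favours the permission. The practical risk is limited to sites that work from Table 27 without applying criterion 1.

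The size is known for itraconazole only: AUC up 51% and C_max up 32%. The dose equivalents assume that this result carries over to repeated dosing in patients. Appendix H does not state the DZD9008 dose used, whether it was single or repeated, or the population. They also assume dose proportionality, which is stated only up to 400 mg. The protocol gives no exposure figure for the other four drugs and no frequency of use for any of the five, so the number of patients at risk cannot be estimated.

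**What to change.** 1. Delete ketoconazole, telithromycin, fluconazole, voriconazole and itraconazole from Table 27. A footnote to Table 23 can record that they may also prolong QT.
2. Reword the lead-in, for example: *These drugs may be used, subject to all other exclusions and restrictions, if the patient has been stable on them for the period shown. For strong CYP3A4 inhibitors, Table 23 and exclusion criterion 1 govern.*
3. Remove Table 27 from the sentence that cites it for withdrawal periods.
4. Send sites a short note now, ahead of the amendment.

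As tidying in the same edit: clarithromycin has a one-week withdrawal in Table 23 but two days in Table 26, so show the longer period. Pimozide, quinidine and thioridazine are allowed with caution in Table 25 but contraindicated in Table 26, so mark them as contraindicated in both.

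The cost is appendix wording in the next amendment and one site communication. The trial design, data collection and analysis do not change.
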